6.4. Data Review Committee

A Data and Safety Review Committee (DRC) will be established to review safety data on a regular basis to ensure safety of all subjects enrolled.

A DRC meeting is to be held at regular intervals to evaluate the safety of this study and other ongoing pediatric studies of ceftaroline fosamil. The role of the DRC members is to evaluate the safety of the pediatric studies on an ongoing basis in order to determine whether any undue safety concerns are observed, and thus whether the studies should be allowed to continue enrollment.

A detailed DRC charter will be prepared by the Investigator and agreed to by all DRC members before initiation of enrollment in this study. This charter will document the timing, membership, analysis content, and review procedures for each DRC meeting. Safety information will be prepared in advance of each DRC meeting. Safety analyses will include, at a minimum, summaries of study disposition and all SAEs, deaths, and discontinuations due to AEs, PCS laboratory results, and individual subject listings of selected safety data.

7. SELECTION, DISCONTINUATION AND WITHDRAWAL OF STUDY SUBJECTS

7.1. Inclusion Criteria

Subjects are required to meet the following inclusion criteria:

1. Informed consent in writing from parent(s) or other legally acceptable representative(s) and assent from subject (if appropriate according to local requirements).
2. Male or female 1 to 17 years of age, inclusive.
3. Suspected hematogenous SA osteomyelitis in a large bone (upper or lower extremities, pelvis) based on clinical findings and radiology results.
4. One to three sites of osteomyelitis with expectation that transition to oral antibiotics will be likely prior to discharge to complete IV therapy (The second or third site might be contiguous like a proximal tibia and distal femur but could also be at sites unrelated such as a distal femur and pelvic bone).
5. Female subjects who have reached menarche must have a negative urine pregnancy test.
6. Female subjects who have reached menarche and are sexually active must be willing to practice sexual abstinence or dual methods of birth control (eg, condom or diaphragm with spermicidal foam or gel) during treatment and for at least 28 days after the last dose of any study drug.
7. Sufficient IV access to receive medication.

7.2.Exclusion Criteria

Subjects must NOT meet any of the following exclusion criteria. Septic arthritis contiguous to the site of osteomyelitis is not an exclusion criterion.

1. Received more than 24 hours of IV antibiotics prior to enrollment.
2. More than three bones infected.
3. Disseminated infection or is admitted to the pediatric intensive care unit.
4. Underlying condition (excludes mild eczema or reactive airways disease).
5. Suspected venous thrombosis or concern for endocarditis.
6. Requirement for other reasons for another antibiotic potentially active against organisms commonly causing osteomyelitis in children.
7. Creatinine clearance < 50 mL/min/1.73m² (calculated by the Schwartz formula)
8. AST or ALT > 3 times the upper limit of normal.
9. Neutropenia (<500 neutrophils/mm³)
10. Thrombocytopenia (<50,000 platelets/mm³)
11. Females who are currently pregnant or breast feeding.
12. Hypersensitivity reaction to any Beta-lactam antibiotic
13. Has had an allergic reaction to ceftaroline in the past.

7.3.Prior and Concomitant Treatment and Medications

All antimicrobials, pain medications, and antipyretics that were taken or received within 14 days before the first dose of study drug and those taken during the study will be recorded. Pain medications such as acetaminophen-codeine, ketorolac, and morphine, will be recorded unless they were used during administration of anesthesia. Medications related to adverse events will be recorded. In addition, each subject's history of pneumococcal vaccinations will be documented, if possible.

7.4.Permitted Treatment and Medications

Concomitant use of the following is permitted: 1) antipyretics as standard of care for fever or symptoms, provided temperature is measured before administration of the antipyretics; 2) Topical antibiotics; and 3) all other concomitant medications and nutrients necessary for the health and well-being of the subject.

7.5. Prohibited Medications and Therapies

Concomitant use of the following is not permitted: 1) potentially effective systemic antibacterial therapy; 2) any drug known to exhibit a contraindicated drug-drug interaction with the study drug; or labeled contraindication to use of oral drug(s); and 3) other cephalosporins/aminoglycosides or other nephrotoxic agents.

7.6. Screening Failures

Subjects who sign and date the ICF but who fail to meet the inclusion and exclusion criteria are defined as screen failures. A screening log will be maintained for all screen failures.

7.7. Subject Discontinuation or Withdrawal

Subjects should be encouraged to complete all study outcome assessments. However, a subject may be discontinued from study drug or may withdraw assent/consent to participate in this study at any time without penalty or loss of benefits to which the subject is otherwise entitled. Subjects will be assessed for safety of ceftaroline at the time points outlined in the schedule of evaluations, if possible.

7.7.1. Off Study Criteria:

- Subjects who require continued home parenteral antibiotics will be discontinued from the study.
- Subjects that require IV treatment after switching to Oral drug.
- If a subject's estimated CrCl decreases to < 50 mL/min during the treatment period, the subject will be discontinued from the study.
- Diarrhea (the occurrence of > 4 loose stools /day) with blood or mucus
- Moderate to severe maculopapular rash that does not resolve following administration of diphenhydramine (Benadryl®) or any urticarial rash.
- Absolute neutrophil count < 500 WBC/mm³ (Grade 4)
- Hemolytic anemia Grade 2 (evidence of > 2 g decrease in hemoglobin but does not require blood transfusion) or above.
- Thrombocytopenia-Platelet count < 100,000/mm³ (Grade 1)
- AST/ALT > 3 X ULN (grade 3)

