3. Suspected hematogenous SA osteomyelitis in a large bone (upper or lower extremities, pelvis) based on clinical findings and radiology results.
4. One to three sites of osteomyelitis with expectation that transition to oral antibiotics will be likely prior to discharge to complete IV therapy (The second or third site might be contiguous like a proximal tibia and distal femur but could also be at sites unrelated such as a distal femur and pelvic bone).
5. Female subjects who have reached menarche must have a negative urine pregnancy test.
6. Female subjects who have reached menarche and are sexually active must be willing to practice sexual abstinence or dual methods of birth control (eg, condom or diaphragm with spermicidal foam or gel) during treatment and for at least 28 days after the last dose of any study drug.
7. Sufficient IV access to receive medication.

Exclusion Criteria: Subjects must **NOT** meet any of the following exclusion criteria. Septic arthritis contiguous to the site of osteomyelitis is not an exclusion criterion.

1. Received more than 24 hours of IV antibiotics prior to enrollment.
2. More than three bones infected.
3. Disseminated infection or is admitted to the pediatric intensive care unit.
4. Underlying condition (excludes mild eczema or reactive airways disease).
5. Suspected or proven venous thrombosis or concern for endocarditis.
6. Requirement for other reasons for another antibiotic potentially active against organisms commonly causing osteomyelitis in children.
7. Creatinine clearance < 50 mL/min/1.73m² (calculated by the Schwartz formula).
8. AST or ALT > 3 times the upper limit of normal.
9. Neutropenia (<500 neutrophils/mm³).
10. Thrombocytopenia (<50,000 platelets/mm³).
11. Females who are currently pregnant or breast feeding.
12. Hypersensitivity reaction to any Beta-lactam antibiotic.
13. Has had an allergic reaction to ceftaroline in the past.

Safety: Adverse event and serious adverse event monitoring, vital signs and laboratory tests (CBC, BUN, Creatinine, Alkaline Phosphatase, Bilirubin, AST and ALT will be obtained within 24 hours prior to enrollment and weekly during ceftaroline treatment and at the completion of ceftaroline treatment). The Alkaline Phosphatase, Bilirubin, AST/ALT results may not be available prior to enrollment of the patient. We do not anticipate that the AST/ALT concentrations will be > 3 UNL but if they were to be this elevated, the subject will be dropped from the study immediately.

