9.3. Study Days 2-14

The total duration of IV ceftaroline is dependent on the subject's response to therapy but 5-14 days is anticipated in most subjects. If the subject is able to switch to oral drug before Day 15, the procedures outlined for Day 15 (EOIV) should be performed. The rest of the visit schedule will be followed as described in Table 2.1.

- Study Drug Administration:

IV ceftaroline fosamil **15 mg/kg** (or 600 mg if > 40 kg) infused over 120 (\pm 10) minutes q8h (\pm 1 hour) for children **2 years of age – 17 years** of age (inclusive).

IV ceftaroline fosamil **10 mg/kg** infused over 120 (\pm 10) minutes q 8h (\pm 1 hour) for children from **1 year of age to < 2 years** (inclusive) until the subject transitions to oral therapy.

- Clinical Assessments – any time during study day (assessments will be performed for research unless they are already being performed per standard of care; exceptions are indicated):
 - Record concomitant medications (Section 8.3). For subjects who are being breast fed, record all medications taken by the lactating mother.
 - Record resting vital signs (pulse, blood pressure, and respiratory rate), and highest postdose temperature measured.
 - Record adjunctive therapeutic procedures (eg, surgeries).
 - Record standard of care radiology results.
 - Evaluate and record physical findings of hematogenous SA osteomyelitis (eg, warmth, tenderness, swelling, erythema, and movement of the infected extremity). Most of the subjects are expected to have surgical incision and drainage procedures and thus assessing the extremity for swelling, erythema, warmth and tenderness may not be possible because of drains in place and large surgical dressings that cannot be removed. The degree of the subject's ability to ambulate will be assessed if the osteomyelitis is in the lower extremity- ie. walks unaided, able to bear weight, can walk aid using a walker, etc. The use of upper and lower extremities will be assessed in terms of movement and range of motion.
 - Identify, assess, and record any new or ongoing AEs or SAEs
- Laboratory Assessments – any time during the study period if clinically indicated (assessments will be performed for research unless they are already being performed per standard of care; exceptions are indicated):
 - Collect CRP and ESR lab results, if clinically indicated.
 - Collect CBC with differential, BUN, and Creatinine, lab results, if clinically indicated.

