to have surgical incision and drainage procedures and thus assessing the extremity for swelling, erythema, warmth and tenderness may not be possible because of drains in place and large surgical dressings that cannot be removed. The degree of the subject's ability to ambulate will be assessed if the osteomyelitis is in the lower extremity- ie. Walks unaided, able to bear weight, can walk aid using a walker, etc. The use of upper and lower extremities will be assessed in terms of movement and range of motion.

- o Assess clinical outcome (site of infection has complete resolution of pain, swelling and warmth and the patient is able to use the affected extremity normally and is back to normal activities).
- o Identify, assess, and record any new or ongoing AEs or SAEs. Subjects will likely remain in the hospital for less than 24 hours once they are transitioned to oral therapy as per standard of care.
- Laboratory Assessments- any time during study day, but before starting PO drug, if applicable. If these assessments are performed within 48 hours of latest results, do not repeat these assessments (assessments will be performed for research unless they are already being performed per standard of care; exceptions are indicated):
 - o Collect CRP and ESR lab results.
 - o Collect CBC with differential, BUN, and Creatinine.
 - o Obtain blood sample for AST, ALT, Alkaline Phosphatase, Bilirubin and Direct Coombs.
 - o If clinically indicated, estimate CrCl using the updated Schwartz "bedside" formula (Schwartz et al, 2009).
 - o Collect results of blood cultures for *S. aureus* only if conducted per standard of care.
 - o Collect purulent material from bone only if a procedure is performed for standard of care when possible.

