12. STATISTICAL ASSUMPTIONS

12.1. Statistical Methods and Planned Analysis

- Descriptive statistical methods will be used to summarize the demographic characteristics of the subjects as well as selected clinical features such as duration of fever or positive blood cultures, time until normalization of ESR and CRP.
- The proportion of children with plasma concentrations of ceftaroline that exceed 1 μ g/mL at 5-6 hours following a 2 hour infusion of ceftaroline dose will be determined.
- Safety analyses will be conducted on all subjects who received at least one dose of ceftaroline.

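### A child with platelets of 50,000 to 99,999/mm³ is eligible under exclusion 10, yet meets the off-study criterion in 7.7.1 at the next blood count even if nothing has changed

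*Combined protocol and SAP*

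**What the plan says.** **Entry.** Exclusion 10 in section 7.2, repeated in the synopsis, reads "Thrombocytopenia (<50,000 platelets/mm³"). A count of 50,000/mm³ or more passes.

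**Off study.** Section 7.7.1 lists "Thrombocytopenia-Platelet count < 100,000/mm³ (Grade 1"). It mentions no baseline value, fall or new onset.

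**Comparable laboratory limits.** The neutrophil limit is the same in both lists: "Neutropenia (<500 neutrophils/mm³") at entry and "Absolute neutrophil count < 500 WBC/mm³ (Grade 4") off study. AST/ALT is above 3 times the upper limit of normal in both. Creatinine clearance is below 50 in both, and the off-study item is worded as a decrease.

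**When counts are taken.** The synopsis and section 12.4 schedule blood tests, including the CBC, "weekly during ceftaroline treatment and at the completion of ceftaroline treatment". Section 9.3 (Days 2-14) says "Collect CBC with differential, BUN, and Creatinine, lab results, if clinically indicated". Section 9.4 lists "Collect CBC with differential, BUN, and Creatinine" at the end of IV treatment, but waives the repeat if results are less than 48 hours old. Table 1.1 footnote 7 relies first on standard-of-care samples, and section 9.8.2 records platelet counts done as standard of care.

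**After withdrawal.** Section 12.1 states: "Safety analyses will be conducted on all subjects who received at least one dose of ceftaroline". Section 7.7 asks for scheduled safety assessments where possible. Section 7.8.3 classes a withdrawn subject who is not a clinical failure as indeterminate at later outcome time points. Section 7.9 replaces only subjects withdrawn before any study drug.

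**The concern.** The two limits disagree over a whole range of counts. Read literally, the protocol enrols a child, starts ceftaroline, and then removes that child because of a value already known at baseline. Unlike AST/ALT, whose results the synopsis says may be unavailable at enrolment, the CBC is not exempted from the pre-dose eligibility assessments.

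For the affected child, the stakes are the remaining ceftaroline days and possibly the outcomes at the end of therapy and at one year. For the trial, they are one unreplaced subject in a sample of 18, and a withdrawal that reflects the entry count and not the drug. Safety is the primary endpoint and section 12.4 summarises discontinuations due to adverse events. The plan does not say how a withdrawal on a pre-existing, unchanged count would be recorded.

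**Working it through.** The plan states no figure to reproduce here, so the check compares the two rules.

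**Step 1: the overlap.** Let P be the platelet count per mm³.

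- Eligible under exclusion 10: P ≥ 50,000.
- Off study under 7.7.1: P < 100,000.
- Both: 50,000 ≤ P ≤ 99,999.

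The off-study limit is 100,000 / 50,000 = 2 times the entry limit. For example, a child entering at 80,000 passes exclusion 10 (80,000 ≥ 50,000). If the next count is again 80,000, the child meets 7.7.1 (80,000 < 100,000) with a change of 0.

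**Step 2: is platelets the exception?**

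| Parameter | Excluded at entry (7.2) | Off study (7.7.1) | Same limit? |
|---|---|---|---|
| Neutrophils | < 500/mm³ | < 500/mm³ | Yes |
| AST/ALT | > 3 × ULN | > 3 × ULN | Yes |
| Creatinine clearance | < 50 | decreases to < 50 | Yes |
| Platelets | < 50,000/mm³ | < 100,000/mm³ | No |

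Platelets are the only one of these four where an eligible baseline value already satisfies the off-study rule. The hemolytic anemia item in 7.7.1 is defined by a hemoglobin fall of more than 2 g, so it too needs a change.

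**Step 3: when would it be triggered?** At the next CBC of any kind. The sections differ on scheduled counts (weekly in the synopsis and 12.4, if clinically indicated in 9.3), and a standard-of-care count can fall on any hospital day. The conflict does not depend on which schedule is followed.

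**Step 4: consequence per child.** One dosed child withdrawn is 1/18 = 5.6% of the sample, not replaced under 7.9. If a site instead applied 7.7.1 to the baseline count before dosing, 7.9 would replace the child. The protocol would then have an unstated entry limit of 100,000.

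**Step 5: effect of one limit.** With exclusion at P < 100,000, eligible means P ≥ 100,000 and off study means P < 100,000. The overlap is empty.

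**The case against.** The strongest reply is that the stricter on-treatment limit is deliberate. Each graded toxicity in 7.7.1 carries its own grade: 1 for platelets, 2 for hemolytic anemia, 4 for neutrophils. The line does not look like a slip for 50,000, and matching limits elsewhere do not oblige platelets to match. That may well be right, but it explains withdrawing a child who falls below 100,000/mm³. It does not explain enrolling one who is already below it.

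A second reply is that the list is about emergent toxicity, since its neighbours (bloody diarrhea, persistent rash, falling creatinine clearance) are events on treatment. This is a sensible reading of intent, but it is not in the text. The creatinine clearance and hemoglobin items state a decrease and the platelet item does not.

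A third reply is that the case is largely theoretical. Exclusions 3 to 5 (disseminated infection or intensive care, underlying conditions, suspected venous thrombosis or concern for endocarditis) plausibly remove many children with low counts. This stands as a limit on size. It does not remove the conflict, because exclusion 10 expressly sets the limit at 50,000/mm³.

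**Conclusion.** The conflict is real, on the plain text, for baseline counts of 50,000 to 99,999/mm³. It is minor. The number of affected children among 18 cannot be computed from the documents and may be zero. Dosed children stay in the safety set, and neither the hypothesis in section 6.2 nor the stopping rules in 7.10 turn on a platelet count.

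Three further inferences are tempting, but the documents do not support them:

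- A reader might take the weekly schedule to cap the loss at about 7 of 14 ceftaroline days. It does not, because a standard-of-care count can trigger the rule on any day.
- A reader might take section 9.4 to guarantee a count at the end of IV treatment. The 48-hour waiver means that it does not.
- A reader might rely on section 7.8.1 to secure follow-up. That section covers discontinuation of study drug, whereas 7.7.1 is an off-study rule. Section 7.8.3 may apply instead and make later outcomes indeterminate. The plan does not say which governs.

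The conclusion assumes that sites follow 7.7.1 as written. An investigator who reads it as new onset would not withdraw the child, but sites should not have to guess.

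**What to change.** Raise the platelet exclusion in section 7.2 and in the synopsis to <100,000/mm³, and leave 7.7.1 unchanged. Entry and off-study limits then agree, as they already do for neutrophils, AST/ALT and creatinine clearance.

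The cost is one line in each of two places at the next amendment, and a few children may become ineligible. A child entering just above 100,000/mm³ could still cross the limit on a small fall, but that is true of any shared threshold.

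A two-tier rule with a percentage fall for children who enter low is not recommended. It needs a percentage that the documents do not supply, and it would relax a safety limit for the children with the lowest counts.

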7.8. Premature Discontinuation From Study Drug Administration

7.8.1. Discontinuations Due to Safety

Assessments and Procedures: A subject who is prematurely discontinued from study drug administration (ie, before the anticipated full course of study drug required for effective treatment of hematogenous SA osteomyelitis *for safety reasons*) should have EOIV or EOT (if on PO drug) assessments conducted per Section 9, and undergo subsequent assessments at FU, if possible. The same procedures will be followed if the subject needs to continue home IV therapy to complete treatment because the subject is intolerant of an appropriate oral antibiotic or there is no oral agent that is active against the organism isolated.

Clinical Outcome Assessment:

If a subject prematurely discontinues the study drug due to an SAE and requires alternative non-study antimicrobials for hematogenous SA osteomyelitis, the subject should be assessed indeterminate.

Reasons: Reason(s) for premature discontinuation from study drug administration *due to safety* may include, but are not limited to, the following:

- Occurrence of an SAE that, in the opinion of the Investigator, warrants the subject's permanent discontinuation from the study drug or oral drug administration.
- Known pregnancy or breastfeeding during the drug administration period. A female subject whose pregnancy test is positive at the end of total treatment must be followed through the immediate postnatal period or until termination of the pregnancy. Every pregnancy will be reported as soon as possible (within 24 hours of learning of the pregnancy), as described in Section 11.1.4.

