7.8.2. Discontinuations Due to Insufficient Therapeutic Effect

Assessments and Procedures: A subject who is prematurely discontinued from study drug administration *due to insufficient therapeutic effect* should have EOIV (if on IV study drug) or EOT (if on PO drug) assessments conducted per Section 9, and undergo subsequent safety assessments at the 4 to 6 week follow up visit. If a subject is discontinued from IV study drug administration *due to insufficient therapeutic effect* and is switched to an alternative IV antibiotic, the alternative therapy should be recorded.

Clinical Outcome Assessment: A subject who is prematurely discontinued from study drug administration *due to insufficient therapeutic effect* should be assessed as a clinical failure on the day of discontinuation. Such a subject will be automatically assigned an outcome of clinical failure at all subsequent evaluation time points.

Reasons: Reason(s) for discontinuation from study drug administration *due to insufficient therapeutic effect* may include, but are not limited to, the following:

- Clinical Worsening: A subject who shows signs of clinical worsening may be prematurely discontinued from study drug administration at any time. If the Investigator deems the benefit-to-risk ratio of continuing study drug acceptable, study drug administration for at least 48 hours is encouraged before discontinuation. If the subject is improving clinically but the blood cultures are persistently positive for *S. aureus* for up to 5 days, ceftaroline can be continued at the discretion of the investigator.
- Lack of Clinical Progress: For a subject who is stable, yet does not show signs of improvement, the Investigator is encouraged to continue study drug administration at least 48 hours before such a subject is assessed as a clinical failure and the subject is prematurely discontinued from study drug.

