9.4. Study Day 15 (End of IV Treatment-EOIV)

The total duration of IV ceftaroline is dependent on the subject's response to therapy but 5-14 days is anticipated in most subjects. If the subject is able to switch to oral drug before Day 15, these procedures may be performed before Day 15. Conduct EOIV assessments within 24 hours after administration of the last dose of IV study drug (subjects will likely remain in the hospital for less than 24 hours once they are transitioned to oral therapy as per standard of care) or at time of premature discontinuation of study drug or early withdrawal from study (if on IV study drug). Conduct the EOIV assessments in place of the regular study visit assessments that would have been performed the day of that visit. A subject may be eligible to switch to PO drug on or after Study Day 3 (Section 9.2). EOIV assessments must occur before starting PO drug. The rest of the visit schedule should be followed as described in Table 2.1.

If applicable, as IV study drug may or may not be given on the same calendar day as EOIV assessments, administer IV study drug IV ceftaroline fosamil **15 mg/kg** (or 600 mg if > 40 kg) infused over 120 (\pm 10) minutes q8h (\pm 1 hour) for children **2 years of age – 17 years** of age (inclusive).

IV ceftaroline fosamil **10 mg/kg** infused over 120 (\pm 10) minutes q 8h (\pm 1 hour) for children from **1 year of age to < 2 years** (inclusive) until the subject transitions to oral therapy.

- Clinical Assessments - any time during study day, but before starting PO study drug, if applicable (assessments will be performed for research unless they are already being performed per standard of care; exceptions are indicated):
 - Record concomitant medications (Section 8.3). For subjects who are being breast fed, record all medications taken by the lactating mother.
 - Record vital signs: resting pulse, blood pressure, and respiratory rate; and highest daily temperature measured.
 - Record adjunctive therapeutic procedures (eg, surgeries).
 - Record standard of care radiology results.
 - Evaluate and record physical findings of hematogenous SA osteomyelitis (eg, warmth, tenderness, swelling, erythema, and movement of the infected extremity). Most of the subjects are expected

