9.7. Follow Up

Conduct FU assessments 12 months after administration of the last dose of the drug (IV or PO whichever is the latest).

- Clinical Assessments - any time during visit (assessments will be performed for research unless they are already being performed per standard of care; exceptions are indicated):
 - o Record concomitant medications (Section 8.3). For subjects who are being breast fed, record all medications taken by the lactating mother.
 - o Record vital signs: resting pulse, blood pressure, respiratory rate and temperature.
 - o Record adjunctive therapeutic procedures (eg, surgeries).
 - o Record standard of care radiology results.
 - o Assess clinical outcome (site of infection has complete resolution of pain, swelling and warmth and the patient is able to use the affected extremity normally and is back to normal activities).
 - o Identify, assess, and record event such as pathologic fractures and growth disturbances.
 - o Laboratory Assessments - any time during visit:

- o If clinically indicated, estimate CrCl using the updated Schwartz "bedside" formula (Schwartz et al, 2009).

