10.5. Collecting and Reporting Adverse Events and Serious Adverse Events

Research related AEs and SAEs are collected from the signing of the informed consent form (ICF) (and assent form, if applicable) until EOT. At Month 12 follow up problems such as pathologic fractures and growth disturbances will be evaluated. The investigational site personnel are to follow unresolved AEs and SAEs at EOT until resolution or stabilization.

At each visit, subjects and/or their parent(s) (or other legally acceptable representative[s]) are to be queried regarding any new or ongoing AEs/SAEs that have occurred since the previous visit. Each, as appropriate, will be asked to volunteer information with a non-leading question such as, for the subjects, "How have you felt since your last visit?" Study center personnel will then record all pertinent information on the appropriate screens of the subject's eCRF.

All research related AEs/SAEs reported by the subject or subject's parent(s) (or legally acceptable representative[s]) or observed or otherwise identified by the Investigator (or other study site personnel) at a defined study visit or during any communication with the subject (or subject's representative[s]) occurring outside a defined study visit must be documented.

All research related AEs must be recorded on the appropriate CRF, whether or not they are considered causally related to the study drug.

For every AE, the Investigator must:

- Provide an assessment of the severity, causal relationship to the study drug), and seriousness of the event (ie, SAE).
- Document all actions taken with regard to the study drug.
- Detail any other treatment measures taken for the AE.

Within 24 business hours of learning of any AE that meets one of the criteria for an SAE, the study center personnel must report the event to Allergan on an SAE/AESI form (Global Patient Safety & Epidemiology Form) and to the FDA and IRB per regulation/local IRB policy.

If, during follow-up, any nonserious AE worsens and eventually meets the criteria for an SAE, that AE should be recorded as a new SAE.

The PI will transmit the SAE/AESI Form to the email and fax number indicated on the most current version of the form. Even if an initial report is made by telephone, an SAE/AESI form completed with all available details must still be emailed/faxed within 24 business hours of knowledge of the event at the study center.

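### Section 7.8.1 names no AE-collecting visit between EOIV and month 12 for a child stopped for safety on IV drug, and conflicts with 7.7 and 10.5

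*Combined protocol and SAP*

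**What the plan says.** Section 7.8.1 covers children who stop study drug for safety reasons. Such a child "should have EOIV or EOT (if on PO drug) assessments conducted per Section 9, and undergo subsequent assessments at FU, if possible". EOT applies only to a child already on oral drug, so a child stopped on IV drug has EOIV and then FU.

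- **EOIV (9.4):** "Conduct EOIV assessments within 24 hours after administration of the last dose of IV study drug", or at premature discontinuation.
- **FU (9.7):** "Conduct FU assessments 12 months after administration of the last dose of the drug". The event item there reads "Identify, assess, and record event such as pathologic fractures and growth disturbances". Section 10.5 agrees: "At Month 12 follow up problems such as pathologic fractures and growth disturbances will be evaluated". The AE/SAE row of Table 1.1 has no mark under Follow-up.

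Section 7.8.2 covers children stopped for insufficient effect. After EOIV or EOT they are to "undergo subsequent safety assessments at the 4 to 6 week follow up visit".

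Three other places bear on the same children:

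- **7.7:** "Subjects will be assessed for safety of ceftaroline at the time points outlined in the schedule of evaluations, if possible".
- **10.5:** "Research related AEs and SAEs are collected from the signing of the informed consent form (ICF) (and assent form, if applicable) until EOT". AEs still open at EOT are followed until they resolve or stabilise.
- **12.8:** data are assessed only until a subject is dropped.

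**The concern.** Safety is the primary objective, and section 6.1 lists AEs and SAEs first among the primary outcome measures. The 4 to 6 week safety assessment is written in for children who stop for lack of effect and left out for children who stop for toxicity. No reason is given.

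If sites follow 7.8.1 as written, how long a child is watched for new AEs depends partly on whether that child has already had one. Section 12.4 tabulates TEAEs, SAEs and discontinuations due to AEs without a cut-off at EOIV, so children observed for different lengths of time are pooled. Section 7.10 also stops the study when two children have severe AEs that the investigator attributes to ceftaroline. A late severe event in a child whose stopping event was not severe would count towards that rule only if someone learned of it.

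**Working it through.** The plan gives no figure for the length of AE follow-up, so there is none to reproduce. The sample-size statement in 6.2 does not bear on this point.

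**Step 1. Scheduled contacts after the last IV dose, by route.**

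| Child | Contacts named | General AE/SAE collection |
|---|---|---|
| Switches to oral drug (Table 1.1, 9.4 to 9.7) | EOIV, post-discharge visits, EOT, 12 months | To EOT |
| Stopped for insufficient effect on IV drug (7.8.2) | EOIV, 4 to 6 weeks | To 4 to 6 weeks |
| Stopped for safety on IV drug (7.8.1 alone) | EOIV, 12 months | To EOIV |
| Needs home IV therapy (7.8.1, 4.5) | As for a safety stop | To EOIV |
| Fully withdrawn (7.8.3) | Day of withdrawal, if possible | To that day |

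**Step 2. Does other text supply the missing visit?** Section 7.7 would, but only where possible, and the toxicity thresholds in 7.7.1 are headed as reasons to be off study. Section 10.5 sets collection to EOT without excepting stopped children, but 7.8.1 uses EOT only for a child on oral drug. A child who stops on IV drug and moves to a non-study antibiotic therefore has no defined EOT. Section 12.8 points towards the short window. The text does not settle the matter.

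**Step 3. Length of the difference.** Let d be the study day of the last IV dose.

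- Under 7.8.1 alone, collection ends by day d + 1 (9.4).
- The comparison is day 28 to day 42. Section 5.2 anticipates EOT at 4 to 6 weeks after enrollment. The 7.8.2 visit is assumed to be counted from enrollment too.
- Difference = 28 − (d + 1) to 42 − (d + 1) days.

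| d (assumed) | Collection ends | Difference |
|---|---|---|
| 3 | day 4 | 24 to 38 days |
| 5 | day 6 | 22 to 36 days |
| 7 | day 8 | 20 to 34 days |
| 14 | day 15 | 13 to 27 days |

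Overall this is 13 to 38 days. If the 4 to 6 weeks ran from discharge, as in the heading of 9.5, the difference would be longer.

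**Step 4. What a missed event does to the tables.** With 18 treated children, one child missed for a given preferred term, or for SAEs, lowers that incidence by 1/18 = 5.6 percentage points. The plan gives no expected rate of safety stops. For an assumed per-child rate p, the chance of at least one among 18 is 1 − (1 − p)^18: 60% at p = 5%, 85% at 10% and 98% at 20%.

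**The case against.** The strongest reply is that the plan already covers these children. Section 7.7 keeps discontinued children under scheduled safety assessment, and 10.5 collects AEs to EOT for everyone. Section 10.5 also requires events learned of outside a visit to be documented and open AEs to be followed until they settle, so a child stopped for toxicity stays in contact until that toxicity resolves or stabilises. The primary objective (5.1) and endpoint (12.2) are set at the end of IV therapy, and EOIV delivers that assessment with AE review, CBC, chemistries and Coombs test.

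Much of this stands. The end-of-IV assessment is intact, and so is follow-up of known events. Table 1.1 schedules no CBC or chemistries after EOIV for any child, so the difference mainly concerns clinically apparent events such as rash or diarrhea. What does not stand is that new events have an assured contact: 7.7 is conditional, EOT is undefined for these children, and 12.8 points the other way.

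A reader might infer more than the documents support:

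- **That children with toxicity have the shortest AE window.** Home-IV children share the path, and withdrawn children are assessed only on the day of withdrawal.
- **That the TEAE rate is biased down.** A child stopped for a treatment-emergent event already counts as having a TEAE. Missing a later event cannot lower that proportion, and with a single arm there is no between-group contrast to distort.
- **That one day of observation can be expressed as a share of a risk period.** That needs constant risk after stopping, which no section supports. AEs in children who switch also arise on oral clindamycin, cephalexin or linezolid, so they are not a clean yardstick for late ceftaroline toxicity.

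**Conclusion.** The point holds as an unreconciled conflict that leaves a gap if 7.8.1 is followed as written. The documents do not establish that these children will go unobserved, because 7.7 and 10.5 can be read the other way.

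The loss is confined to new or delayed AEs between EOIV and the time when other children reach EOT or the 4 to 6 week visit. It can lower counts of further event types and of SAEs, by 5.6 points for each child missed.

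The 13 to 38 days rest on three assumptions: the last IV dose falls on days 3 to 14, EOIV is done within a day of it, and the 4 to 6 weeks run from enrollment. How many of the 18 children would be affected cannot be determined from the plan.

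**What to change.** Reconcile 7.7, 7.8.1, 7.8.2, 10.5 and 12.8.

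- **7.8.1:** add the 4 to 6 week safety assessment that 7.8.2 already has, by visit or telephone, and say from which date the weeks are counted.
- **10.5:** state one end point of AE/SAE collection for every treated child who has not withdrawn consent. Name children taken off under 7.7.1 and home-IV children as included, and do not rely on EOT where it is undefined.
- **7.7 and 12.8:** align both with that end point, so that coming off study drug or off study does not by itself end AE collection.

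The cost is a short amendment and one extra contact for a few children. The AE count may rise slightly. The sample size stays at 18.
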